12.2. Appendix 2: Clinical Laboratory Tests

The tests and calculations detailed in [Table 4](#) and [Table 5](#) will be performed by the central laboratory or (for calculated values) by GSK. Local laboratory results are required in the event that a participant has a haemoglobin of <90g/L or a platelet count of <100x10⁹/L during the dosing period (Day 1 to Day 71). A local laboratory result may also be acceptable with pre-approval by GSK.

In circumstances where it is not possible to obtain bloods at site or ship bloods to the central lab due to the COVID-19 pandemic, scheduled safety (standard hematology and clinical chemistry) labs and pregnancy tests for the Day 113, Day 155, Day 197 and Early Withdrawal (if required) visits should be performed if feasible and may be performed locally at the clinical site or within the community (all at the discretion of the Investigator).

If a local sample is required for haemoglobin or platelet count, the results must be entered into the eCRF. A simultaneous unscheduled sample should also be sent for central analysis.

The tests detailed in [Table 4](#) and [Table 5](#) represent a minimum set of assessments and this list may be expanded if determined necessary by the sponsor.

Additional tests may be performed at any time during the study as determined necessary by the investigator or required by local regulations.

Table 4 Safety Laboratory Assessments

Laboratory Assessments	Parameters		
Standard Hematology	RBC Count Haemoglobin Haematocrit MCV MCH MCHC RDW	Platelet Count Mean Platelet Volume Reticulocyte Percentage Absolute Reticulocyte Count Reticulocyte Production Index ¹	WBC count with Differential: Neutrophils Lymphocytes Monocytes Eosinophils Basophils
Clinical Chemistry ²	Potassium Sodium Corrected Calcium At screening only³ TSH FT4	Aspartate Aminotransferase (AST) Alanine Aminotransferase (ALT) Alkaline Phosphatase (ALP) Lactate Dehydrogenase (LD) Lipids (fasted)⁴ Total Cholesterol HDL	Urea Creatinine eGFR ⁵ Glucose ⁶ Total bilirubin Direct bilirubin Albumin Total Protein

Laboratory Assessments	Parameters		
	FT3 INR APTT	LDL Triglycerides	
Routine Urinalysis	
 Specific gravity, pH, glucose, protein, blood, ketones by dipstick Microscopic examination (if blood or protein is abnormal) 		
Other Screening Tests	
 Follicle-stimulating hormone and estradiol (as needed in women of non-childbearing potential only) Serum or urine human chorionic gonadotropin pregnancy test (as needed for women of childbearing potential)⁷ Serology (HIV antibody, HBsAg, HBcAb and hepatitis C virus antibody) QuantiFERON-TB Gold / QuantiFERON-TB Gold PLUS 		

NOTES :

1. Calculated value based on reticulocyte percentage/count and haematocrit.
2. Details of liver chemistry stopping criteria and required actions and follow-up assessments after liver stopping or monitoring event are given in Section 8.1.2 and Appendix 7. All events of ALT $\geq 3 \times$ upper limit of normal (ULN) and bilirubin $\geq 2 \times$ ULN (>35% direct bilirubin) or ALT $\geq 3 \times$ ULN and international normalized ratio (INR) >1.5 , if INR measured, which may indicate severe liver injury (possible Hy's Law), must be reported as an SAE (excluding studies of hepatic impairment or cirrhosis).
3. Blood for TSH, FT4, FT3, INR and APTT will be taken at screening only.
4. Blood for lipid tests (fasted) will be taken at predose on Day 1 and Day 85 (Week 12) only.
5. Calculated value. Estimated GFR will be calculated using the MDRD formula.
6. Glucose on Day 1 and Day 85 will be fasted glucose, all other timepoints will be random glucose.
7. Serum pregnancy testing will be performed at screening, Day 197 (Week 28) and early withdrawal visit and urine pregnancy testing will be performed at all other visits unless serum testing is required by local regulation or IRB/IEC. Pregnancy testing on dosing days must be performed prior to administration of study treatment. If it is not possible for a serum pregnancy test to be performed due to the COVID-19 pandemic, a urine pregnancy test should be performed if possible.

Table 5 Additional Haematology Assessments

Time Point	Parameters
Screening, Day 1, Day 85 (Week 12) and Day 197 (Week 28) AND if any haematology stopping rule (at the next visit) OR early withdrawal is fulfilled	Serum Ferritin % Transferrin saturation Serum B12 Serum folate
Day 1, Day 85 (Week 12) and Day 197 (Week 28)	Serum Haptoglobin TPO EPO

Time Point	Parameters
AND if any haematology stopping rule (at the next visit) OR early withdrawal is fulfilled	
Day 1 and Day 85 (Week 12)	Blood Film

To maintain blinding only results of safety laboratory assessments will be reported to the investigative sites or other blinded personnel. No other laboratory data (e.g. PK, target engagement and biomarkers) will be provided until study completion.

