Baseline Assessments												
Autoantibodies	X ¹											
Medical History ²	X ¹											
Safety Assessments and Cardiac Monitoring												
Complete Physical Exam	X ¹										X	X
Brief Physical Exam		X	X	X	X	X	X	X	X			
Vital Signs (blood pressure, heart rate, temperature)	X ¹	X ¹	X ¹	X ¹	X ¹	X ¹	X	X	X	X	X	X
12 –lead ECG (triplicate at day 1 or if QTc abnormal)	X ¹	X ¹			X ¹							
AE/SAE Review ^{3, 13}	Continuous throughout study											
Concomitant Medication Review ¹³	Continuous throughout study											
Serum Pregnancy Test (WOCBP) ¹³											X ¹⁴	X ¹⁴
Urine Pregnancy Test (WOCBP) ¹³	X ¹	X ¹	X ¹	X ¹	X ¹	X ¹	X	X	X			
Standard Haematology/Clinical Chemistry (see Appendix 2) ¹³	X ^{1, 4}	X	X	X	X	X	X ⁴	X	X	X	X	X

2016N269831_05

CONFIDENTIAL

201247

Procedure	Treatment Period (Days)							Day 113 ± 5 days	Day 155 ± 10 days	Day 197 ± 10 days (Final Follow -Up)	Early Withdrawal ¹³ (refer Section 8.2)
	Day 1	Day 15 ± 2 days	Day 29 ± 2 days	Day 43 ± 2 days	Day 57 ± 2 days	Day 71 ± 3 days	Day 85 ± 3 days				
Study Week		W2	W4	W6	W8	W10	W12	W16 ¹³	W22 ¹³	W28 ¹³	
Additional Haematology (see Appendix 2 for list)	X ¹						X			X	X
Urinalysis	X ¹						X			X	X
Pharmacokinetics, Pharmacodynamics, Immunogenicity and Genetics											
Optional Suction Blister ⁵					←-----X-----→						
Immunogenicity Sampling	X ¹	X			X		X			X	X
Pharmacokinetic Blood Sampling	X ¹	X	X		X		X	X	X	X	X
Target Engagement (OSM) Blood Sampling	X ¹	X	X		X		X	X	X	X	X
Genetic Sampling ⁶	X										
Disease markers (efficacy) Assessment											
Skin Biopsy	X ¹						X ⁷				X ⁸
Blood Biomarkers (see Section 9.8.1)	X ^{1,9}		X		X		X ⁹			X	
C-reactive protein (CRP)	X ¹	X	X		X		X	X		X	X
mRSS	X ¹				X		X			X	X ¹⁰
Respiratory Laboratory FVC	X ¹						X			X	X ¹⁰
Home Spirometry FVC ¹¹	←-----weekly-----→										
SHAQ /PhGA/PtGA/CRIS data ¹²	X ¹						X			X	

2016N269831_05

CONFIDENTIAL

201247

1. To be performed pre-dose.
2. Medical history will include smoking history and information regarding the participant's most recent HRCT scan if available. Medical occurrences that begin before the start of study treatment (Day 1) but after obtaining informed consent will be recorded as medical history.
3. SAEs will be recorded from signing of informed consent; AEs will be recorded from administration of first study treatment.
4. Day 1 predose sample and Day 85 (Week 12) will be fasted and include lipid assessments.

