6.3. Lifestyle Restrictions**6.3.1. Meals and Dietary Restrictions**

Participants will be required to fast for 12 hours (no food or drink, except water) prior to collection of the Day 1 and Day 85 (Week 12) clinical chemistry blood sample. There will be no other caffeine, xanthine or dietary restrictions for the rest of the study.

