5.3. Baseline Definitions

The column 'Baseline Label Used in Data Display' shows the preferred baseline for a parameter but if this is missing or a later, unscheduled, assessment exists then the latest pre-dose assessment will be used for that participant unless otherwise specified. If time is not collected, Day 1 assessments are assumed to be taken prior to first dose and used as baseline unless otherwise specified.

Parameter	Study Assessments Considered as Baseline		Baseline Label Used in Data Display
	Screening	Day 1 (Pre-Dose)	
Primary endpoints			
Safety			
12-Lead ECG		X	Day 1 (Pre-Dose)
			[Note: Triplicate]
Vital Signs		Х	Day 1 (Pre-Dose)
Lab		Х	Day 1 (Pre-Dose)
Urinalysis		Х	Day 1 (Pre-Dose)
Secondary endpoints			
PD			
Serum OSM free and total		X	Day 1 (Pre-Dose)
Blister OSM total No baselir		No baseline	
РК			
Plasma PK		Х	Day 1 (Pre-Dose)
Blister PK			No baseline
Immunogenicity			
Immunogenicity		Х	Day 1 (Pre-Dose)
Exploratory endpoints			
Efficacy			
mRSS		X	Day 1 (Pre-Dose)
Respiratory Laboratory FVC		Х	Day 1 (Pre-Dose)
Home Spirometry FVC		X[1]	Day 1
SHAQ /PhGA /PtGA /CRISS ^[2]		X	Day 1 (Pre-Dose)
Disease biomarkers			
CRP		X	Day 1 (Pre-Dose)
Blood biomarkers		X	Day 1 (Pre-Dose)
Biopsy mRNA		X	Day 1 (Pre-Dose)
Biopsy IHC		X	Day 1 (Pre-Dose)

201247

Parameter	Study Assessments Considered as Baseline		Baseline Label Used in Data Display
	Screening	Day 1 (Pre-Dose)	
Mechanistic haematology		Х	Day 1 (Pre-Dose)

NOTES:

1: The day 1 Home Spirometry FVC (which will be taken on site) is not mandated by the protocol to be pre-dose. If the home spirometry is taken post Day 1 dose, then the latest screening observation prior to dosing will be used as baseline.

2: CRISS is a measure of change and events over a time period, starting at Day 1.

• Unless otherwise stated, the mean of replicate assessments at any given time point will be used as the value for that time point.

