3.9.	Safety	AE1	Summary of Serious Adverse Events by System Organ Class and Preferred Term, by Treatment Phase	For IA1, don't present by phase and remove ', by Treatment Phase' from the title. Add a row to include number of participants contributing to treatment phase and use as denominator. Add footnote 'Note: On treatment phase defined as period from first dose to last dose + 28 days. Follow up phase defined as period after last dose + 28 days.'	IA1, IA2, SAC		

Safety: Tables						
No.	Population	IDSL / TST ID / Example Shell	Title	Programming Notes	Deliverable	
3.10.	Safety	AE16	Summary of Serious Adverse Events by System Organ Class and Preferred Term (Number of Subjects and Occurrences)		SAC	
3.11.	Safety	AE3	Summary of Serious Drug-Related Adverse Events, by Treatment Phase	Add a row to include number of participants contributing to treatment phase and use as denominator.	SAC	
3.12.	Safety	AE1	Summary of Adverse Events Leading to Permanent Discontinuation of Study Treatment or Withdrawal from Study by System Organ Class and Preferred Term, by Treatment Phase	Add footnote 'Note: On treatment phase defined as period from first dose to last dose + 28 days. Follow up phase defined as period after last dose + 28 days.'	SAC	
3.13.	Safety	AE3	Summary of Non-Fatal Drug-Related Serious Adverse Events, by Treatment Phase	Add a row to include number of participants contributing to treatment	SAC	
3.14.	Safety	AE3	Summary of Fatal Drug-Related Serious Adverse Events, by Treatment Phase	phase and use as denominator. Add footnote 'Note: On treatment phase defined as period from first dose to last dose + 28 days. Follow up phase defined as period after last dose + 28 days '		
Chemis	try					
3.15.	Safety	LB1	Summary of Chemistry		IA1, IA2, SAC	
3.16.	Safety	LB1	Summary of Change from Baseline in Chemistry		IA1, IA2, SAC	
3.17.	Safety	LB1	Summary of Percentage Change from Baseline in Chemistry		IA1, IA2, SAC	
3.18.	Safety	LB17	Summary of Worst-Case Chemistry Results Relative to Potential Clinical Importance (PCI) Criteria Post-Baseline Relative to Baseline		DEC, SAC	
Haemat	ology					

Safety:	Tables				
No.	Population	IDSL / TST ID / Example Shell	Title	Programming Notes	Deliverable

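### Glucose is fasted at baseline but random at 8 of 9 scheduled post-baseline visits, and the planned chemistry change and worst-case tables do not separate the two sample types

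*Protocol*

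**What the plan says.** **Sampling.** Protocol Appendix 2, note 6 to Table 4: "Glucose on Day 1 and Day 85 will be fasted glucose, all other timepoints will be random glucose". Protocol section 6.3.1 agrees: participants must "fast for 12 hours (no food or drink, except water) prior to collection of the Day 1 and Day 85 (Week 12") chemistry sample, and there is no other dietary restriction. Note 4 to the Schedule of Activities says the same: "Day 1 predose sample and Day 85 (Week 12) will be fasted and include lipid assessments". The schedule row "Standard Haematology/Clinical Chemistry (see Appendix 2") is marked at Day 1, at nine later visits, and at Early Withdrawal.

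**Baseline.** SAP section 5.3 lists laboratory tests with Day 1 pre-dose as baseline and makes no exception for glucose. The baseline column "shows the preferred baseline for a parameter but if this is missing", or if a later unscheduled pre-dose value exists, the latest pre-dose value is used.

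**Displays.** SAP Appendix 12, section 16.12.5, plans:
- Table 3.16, "Summary of Change from Baseline in Chemistry"
- Table 3.17, "Summary of Percentage Change from Baseline in Chemistry"
- Table 3.18, "Summary of Worst-Case Chemistry Results Relative to Potential Clinical Importance (PCI) Criteria Post-Baseline Relative to Baseline"

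None of the three has a programming note on glucose. SAP section 16.8.2 gives one pair of glucose limits, below 3 and above 9 mmol/L. SAP section 7.2 runs the worst-case period from first dose to final follow-up.

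**The concern.** A change from baseline is interpretable when both samples were taken under the same conditions. Here the baseline follows a 12-hour fast, and most post-baseline samples carry no fasting instruction. Any average difference between a random and a fasted sample enters the within-arm change at every random visit and drops out at Day 85. The worst-case table selects the most extreme value from a pool that is mostly random and compares its category with that of a fasted baseline.

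Clinical chemistry is among the primary safety endpoints. Protocol section 10.3.1 plans no formal testing and relies on review of displays, so a misleading row has no later analysis to correct it. A high random value would also bring the participant into Listing 25, which shows all laboratory data for anyone with a value of potential clinical importance.

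Lipids do not share the problem, because they are measured only at the two fasted visits.

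**Working it through.** The plan gives no figure on this point to reproduce. The check is a count, a short piece of algebra, and an illustration whose inputs are assumptions.

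**1. Sample type by visit** (Schedule of Activities with note 6)

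| Visit | Glucose sample |
|---|---|
| Screening | random |
| Day 1 (baseline) | fasted |
| Days 15, 29, 43, 57, 71 | random |
| Day 85 | fasted |
| Days 113, 155, 197 | random |

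Scheduled post-baseline visits: 5 + 1 + 3 = 9. Random: 5 + 3 = 8. Fasted: 1. An Early Withdrawal sample would be one more random sample.

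**2. What the change measures.** Let δ be the mean random-minus-fasted difference. At a random visit, expected within-arm change = true change + δ. At Day 85 it is the true change alone. Active minus placebo at a random visit = difference in true changes + (δ active − δ placebo). The last bracket is 0 in expectation if δ is the same in both arms.

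**3. Illustration (assumed values, none in the documents).** Take mean fasted glucose 5.0 mmol/L, within-subject fasted SD 0.3 and random-sample SD 1.0. The SD of one participant's change is √(1.0² + 0.3²) = 1.044. With no true change, the probability that an arm's observed mean change is above 0 at one random visit is Φ(δ√n / 1.044).

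| Assumed δ (mmol/L) | δ / 5.0 | n = 15 | n = 5 | n = 3 |
|---|---|---|---|---|
| 0 | 0% | 0.50 | 0.50 | 0.50 |
| 0.3 | 6% | 0.87 | 0.74 | 0.69 |
| 0.5 | 10% | 0.97 | 0.86 | 0.80 |
| 1.0 | 20% | 1.00 | 0.98 | 0.95 |
| 1.5 | 30% | 1.00 | 1.00 | 0.99 |

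Here 15 and 5 are the active and placebo numbers in a cohort 2 of 20, and 3 is the active number among the first four in cohort 1. An apparent rise is likely if δ is sizeable. It is not certain at each visit in small arms, and there is none to expect if δ is 0.

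**4. Worst-case flag.** If one random sample exceeds 9 mmol/L with assumed probability p, independently across visits, at least one of eight does so with probability 1 − (1 − p)⁸. This is 3.9% for p = 0.5%, 7.7% for 1%, 14.9% for 2% and 33.7% for 5%.

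**5. Is the Day 85 row itself clean?** Not always.
- SAP Appendix 3, Table A, slots unscheduled and early-withdrawal chemistry from Days 79 to 99 into Day 85. Under note 6 such a sample is random. It can supply the Day 85 value when the scheduled sample is missing or lies further from the target day.
- If Day 1 is missing, the fallback baseline may be the screening value, which is random. The Day 85 comparison then becomes the mismatched one.

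**6. Does the SAP handle similar cases?** Yes. Section 13.1.1 reports C1M separately by assay kit, and it excludes insufficient alpha SMA samples from the main summaries. Glucose has no comparable rule.

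**The case against.** A reader might infer that the tables will show glucose rising in every arm from Day 15, returning at Day 85 and rising again at Day 113. The documents do not support that. They give no fasted-to-random difference, no direction, and no meal or clock time for the visits. A random sample need not follow a meal, and small arms need not show a rise at each visit.

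A reader might also infer a built-in treatment signal. That does not follow either. Placebo participants are sampled on the same schedule, so an equal shift cancels in expectation. What remains is misleading within-arm change and added noise. Planned placebo numbers are small: about 6 at the minimum (1 + 5) and about 10 if all 40 are randomised.

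Three further points limit the weight of the concern, and they stand:
- Glucose is not a named risk, has no stopping rule and is not in the chemistry figures.
- Protocol section 10.3.1 makes investigator-reported relationship to product the principal consideration for safety.
- The end-of-treatment comparison, Day 85 against Day 1, is like-for-like when both scheduled samples exist.

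SAP section 7.2 also relies on the sponsor's core data standards, and non-standard display shells are in a separate document. Those might separate the two sample types. They are not available here and the SAP does not say that they do, so they cannot be assumed to solve the problem.

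**Conclusion.** The mismatch is established from the documents: 8 of 9 scheduled post-baseline glucose changes compare a random sample with a fasted baseline, and the worst-case table pools both types against one range. Within-arm changes at those visits, and the worst-case shifts, may show an apparent change unrelated to treatment. Its size and direction cannot be derived from the documents; the illustrations above rest wholly on assumed values. The active-versus-placebo reading is protected in expectation if the random-minus-fasted difference is the same in both arms, though only roughly balanced in samples this small.

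This is a minor point affecting one analyte in descriptive safety tables. It is worth correcting because those displays are the planned safety analysis and the correction is cheap.

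**What to change.** In SAP section 5.3 and Appendix 12, define fasted glucose and random glucose as separate parameters.

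- **Tables 3.16 and 3.17:** show glucose change and percentage change only for fasted Day 85 against fasted Day 1. Keep random unscheduled or early-withdrawal samples slotted to Day 85, and any random screening value used as fallback baseline, out of that row.
- **Other visits:** report random glucose as absolute values, labelled as random, without change from the Day 1 baseline.
- **Table 3.18:** give fasted and random glucose separate rows, and label the sample type to which the concern range is applied.

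Using the random screening value as baseline for the random visits is not a good alternative. It can be up to 42 days old and is equally uncontrolled for meals. It can also precede the 4-week corticosteroid stability period required before Day 1. It would put two baselines into one worst-case table, and a post-baseline value above 9 mmol/L would still count as a shift to high from any in-range screening value.

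**Cost:** SAP wording and one derived parameter, with no new data, since note 6 assigns sample type by visit. The loss is that glucose has no change-from-baseline figure at the eight random visits.

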12.3. Appendix 3: Study Governance Considerations

Regulatory and Ethical Considerations

- This study will be conducted in accordance with the protocol and with:
 - Consensus ethical principles derived from international guidelines including the Declaration of Helsinki and Council for International Organizations of Medical Sciences (CIOMS) International Ethical Guidelines
 - Applicable ICH Good Clinical Practice (GCP) Guidelines
 - Applicable laws and regulations
- The protocol, protocol amendments, ICF, Investigator Brochure, and other relevant documents (eg, advertisements) must be submitted to an IRB/IEC by the investigator and reviewed and approved by the IRB/IEC before the study is initiated.
- Any amendments to the protocol will require IEC/IRB approval before implementation of changes made to the study design, except for changes necessary to eliminate an immediate hazard to study participants.
- The investigator will be responsible for the following:
 - Providing written summaries of the status of the study to the IRB/IEC annually or more frequently in accordance with the requirements, policies, and procedures established by the IRB/IEC
 - Notifying the IRB/IEC of SAE or other significant safety findings as required by IRB/IEC procedures
 - Providing oversight of the conduct of the study at the site and adherence to requirements of 21 CFR, ICH guidelines, the IRB/IEC, European regulation 536/2014 for clinical studies (if applicable), and all other applicable local regulations

Financial Disclosure

Investigators and sub-investigators will provide the sponsor with sufficient, accurate financial information as requested to allow the sponsor to submit complete and accurate financial certification or disclosure statements to the appropriate regulatory authorities. Investigators are responsible for providing information on financial interests during the course of the study and for 1 year after completion of the study.

Informed Consent Process

- The investigator or his/her representative will explain the nature of the study to the participant or his/her legally authorized representative and answer all questions regarding the study.
- Participants must be informed that their participation is voluntary. Participants or their legally authorized representative will be required to sign a statement of

informed consent that meets the requirements of 21 CFR 50, local regulations, ICH guidelines, Health Insurance Portability and Accountability Act (HIPAA) requirements, where applicable, and the IRB/IEC or study center.

- The medical record must include a statement that written informed consent was obtained before the participant was enrolled in the study and the date the written consent was obtained. The authorized person obtaining the informed consent must also sign the ICF.
- Participants must be re-consented to the most current version of the ICF(s) during their participation in the study.
- A copy of the ICF(s) must be provided to the participant or the participant's legally authorized representative.
- Participants who are rescreened are required to sign a new ICF.

The ICF will contain a section that addresses the use of remaining samples for exploratory research. Participants will be told that they may withdraw their consent at any time and for any reason during the storage period.

Data Protection

- Participants will be assigned a unique identifier by the sponsor. Any participant records or datasets that are transferred to the sponsor will contain the identifier only; participant names or any information which would make the participant identifiable will not be transferred.
- The participant must be informed that his/her personal study-related data will be used by the sponsor in accordance with local data protection law. The level of disclosure must also be explained to the participant.
- The participant must be informed that his/her medical records may be examined by Clinical Quality Assurance auditors or other authorized personnel appointed by the sponsor, by appropriate IRB/IEC members, and by inspectors from regulatory authorities.

Committees Structure

